### **8.3.1. Time Period and Frequency for Collecting Adverse Event and Serious Adverse Event Information**

#### **All Adverse Events**

All AEs and special reporting situations, whether serious or non-serious, will be reported from the time a signed and dated ICF is obtained until completion of the participant's last study-related procedure, which may include contact for follow-up of safety.

#### **Serious Adverse Events**

All SAEs, as well as PQC s, occurring during the study must be reported to the appropriate sponsor contact person by study-site personnel immediately, but no later than 24 hours of their knowledge of the event.

Serious adverse events, including those spontaneously reported to the investigator within 4 weeks after the last administration of study intervention, must be reported. The sponsor will evaluate any safety information that is spontaneously reported by an investigator beyond the time frame specified in the protocol.

A **possible Hy's law case** is defined by the occurrence of ALT/AST  $\geq 3 \times$  ULN, alkaline phosphatase (ALP)  $< 2 \times$  ULN together with total bilirubin (Tbili)  $\geq 2 \times$  ULN or INR  $> 1.5$  (if measured). Any possible Hy's Law case is considered an important medical event and should be reported to the sponsor in an expedited manner, even before all other possible causes of liver injury have been excluded. See Section 10.6, Appendix 6: Liver Safety: Suggested Actions and Follow-up Assessments for more details.

Information regarding SAEs will be transmitted to the sponsor using a SAE reporting form and safety report form of the eCRF, which must be completed and reviewed by a physician from the study site and transmitted in a secure manner to the sponsor within 24 hours. The initial and follow-up reports of a SAEs should be transmitted in a secure manner electronically or by facsimile (fax). Telephone reporting should be the exception and the reporter should be asked to complete the appropriate form(s) first.

### **8.3.2. Method of Detecting Adverse Events and Serious Adverse Events**

Care will be taken not to introduce bias when detecting AEs or SAEs. Open-ended and nonleading verbal questioning of the participant is the preferred method to inquire about AE occurrence.

#### **Solicited Adverse Events**

Solicited AEs are predefined local and systemic events for which the participant is specifically questioned.

## **Unsolicited Adverse Events**

Unsolicited AEs are all AEs for which the participant is not specifically questioned.

### **8.3.3. Follow-up of Adverse Events and Serious Adverse Events**

The investigator is obligated to perform or arrange for the conduct of supplemental measurements and evaluations as medically indicated to elucidate the nature and causality of the AE, SAE, or PQC as fully as possible. This may include additional laboratory tests or investigations, histopathological examinations, or consultation with other health care professionals.

Adverse events, including pregnancy, will be followed by the investigator as specified in Section 10.4 Appendix 4; Adverse Events, Serious Adverse Events, Product Quality Complaints, and Other Safety Reporting: Definitions and Procedures for Recording, Evaluating, Follow-up, and Reporting.

### **8.3.4. Regulatory Reporting Requirements for Serious Adverse Events**

The sponsor assumes responsibility for appropriate reporting of AEs to the regulatory authorities. The sponsor will also report to the investigator (and the head of the investigational institute where required) all suspected unexpected serious adverse reactions (SUSARs). The investigator (or sponsor where required) must report SUSARs to the appropriate Independent Ethics Committee (IEC)/IRB that approved the protocol unless otherwise required and documented by the IEC/IRB. A SUSAR will be reported to regulatory authorities unblinded. Participating investigators and IEC/IRB will receive a blinded SUSAR summary, unless otherwise specified.

### **8.3.5. Pregnancy**

All initial reports of pregnancy in female participants or partners of male participants must be reported to the sponsor by the study-site personnel within 24 hours of their knowledge of the event using the appropriate pregnancy notification form. Abnormal pregnancy outcomes (eg, spontaneous abortion, fetal death, stillbirth, congenital anomalies, ectopic pregnancy) are considered SAEs and must be reported using the Serious Adverse Event form. Participants who are found to be pregnant in between study visits should immediately stop taking the study intervention and contact the investigator.

Follow-up information regarding the outcome of the pregnancy and any postnatal sequelae in the infant will be required.

### **8.3.6. Disease-Related Events and Disease-Related Outcomes Not Qualifying as Adverse Events or Serious Adverse Events**

All events that meet the definition of a SAE will be reported as SAEs, regardless of whether they are protocol-specific assessments.

### **8.3.7. Adverse Events of Special Interest**

An adverse event of special interest (AESI; serious or non-serious) is one of scientific and medical concern specific to the sponsor's product or program, for which ongoing monitoring and expedited

communication (within 24 hours) by the investigator to the sponsor is warranted. The AESIs for JNJ-77242113 are active TB, malignancy, and potential Hy's Law cases.

A possible Hy's law case is defined by the occurrence of ALT/AST  $\geq 3 \times$  ULN, together with Tbili  $\geq 2 \times$  ULN or INR  $>1.5$  (if measured). Any possible Hy's Law case is considered an important medical event and should be reported to the sponsor in an expedited manner using the AESI form, even before all other possible causes of liver injury have been excluded ([FDA 2009](#)).

A confirmed Hy's law case must be reported as a SAE.

Any newly identified malignancy, case of active TB, or potential Hy's law case occurring after the first study intervention administration(s) must be reported by the investigator according to the procedures for SAE reporting in Section 10.4, Appendix 4; Adverse Events, Serious Adverse Events, Product Quality Complaints, and Other Safety Reporting: Definitions and Procedures for Recording, Evaluating, Follow-up, and Reporting. Investigators are also advised that active TB is considered a reportable disease in most countries. These events are to be considered serious only if they meet the definition of an SAE.

#### **8.4. Pharmacokinetics**

Plasma samples will be used to evaluate the PK of JNJ-77242113. Plasma collected for PK may additionally be used to evaluate safety or efficacy aspects that address concerns arising during or after the study period. Genetic analyses will not be performed on these serum samples. Participant confidentiality will be maintained.

##### **8.4.1. Evaluations**

Venous blood samples will be collected for measurement of plasma concentrations of JNJ-77242113 at timepoints indicated in the SoA (Section 1.3). During the study, the nominal sample collection times may be changed by the sponsor with clear communication to the investigator, but the total blood volume will not exceed 450 mL every 8 weeks. The exact dates and times of blood sample collection must be recorded on the laboratory requisition form.

The laboratory manual contains further information regarding the collection, handling, labeling, and shipment of plasma samples.

##### **8.4.2. Analytical Procedures**

###### **Pharmacokinetics**

Plasma JNJ-77242113 liquid chromatography/mass spectrometry/mass spectrometry (LC-MS/MS)

##### **8.4.3. Pharmacokinetic Parameters and Evaluations**

###### **Parameters**

Based on the individual plasma concentration-time data, using the actual dose taken and the actual sampling times, PK parameters and exposure information of JNJ-77242113 will be derived using

population PK modeling. Baseline covariates (eg, body weight, age, sex, CrCL, race) may be included in the model, if relevant.

Pharmacokinetic analysis will be performed by or under the responsibility of the sponsor.

Using the actual sampling times (see the SoA, Section 1.3), if feasible, the following PK parameters will be estimated for JNJ-77242113 using a population PK approach:

$C_{\max}$	Maximum observed plasma analyte concentration.
$C_{\text{trough}}$	Plasma concentration just prior to the beginning or at the end of a dosing interval.
$t_{\max}$	Actual sampling time to reach the maximum observed plasma analyte concentration.
$AUC_{24h}$	Area under the plasma analyte concentration-time curve from time 0 to 24 hours postdose, calculated by linear-linear trapezoidal summation.
$AUC_{\text{last}}$	Area under the plasma analyte concentration vs time curve from time 0 to time of the last measurable (non-below quantification limit [BQL]) concentration calculated by linear-linear trapezoidal summation.
$AUC_{\infty}$	Area under the analyte concentration vs. time curve from time 0 to infinite time, calculated as $AUC_{\text{last}} + C_{\text{last}}/\lambda_z$ , where $C_{\text{last}}$ is the last observed measurable (non-BQL) plasma analyte concentration; extrapolations of more than 20.00% of the total AUC are reported as approximations.
$t_{1/2}$	Apparent elimination half-life calculated as $0.693/\lambda_z$ .
$\lambda_z$	Apparent terminal elimination rate constant, estimated by linear regression using the terminal log-linear phase of the log transformed concentration-time curve.

## 8.5. Genetics and Pharmacogenomics

This section is not applicable to this study.

## 8.6. Biomarkers

Biomarker assessments will be used to define and identify PD markers of therapeutic response to better understand the mechanism of action of JNJ-77242113 in participants with psoriasis and aid in evaluating the drug exposure-clinical response relationship. These assessments will include evaluation of relevant disease and pathway engagement biomarkers in serum, skin (optional substudy), and whole blood (optional substudy). These assessments could also help explain interindividual variability, including differences between responders and non-responders to support patient stratification. Biomarker samples may also be used to help address emerging issues and to enable the development of safer, more effective, and ultimately individualized therapies as well as development of tests/ assays related to JNJ-77242113 and psoriasis.

Biomarker samples will be collected per the SoA (Section 1.3). Instructions for collection and shipment of samples will be outlined in the Laboratory and Biopsy reference manuals and will include the following assessments.

### Stopping Analysis

Biomarker analyses are dependent upon the availability of appropriate biomarker assays and clinical response rates. Biomarker analysis may be deferred or not performed, if during or at the end of the study, it becomes clear that the analysis will not have sufficient scientific value for

biomarker evaluation, or if there are not enough samples or responders to allow for adequate biomarker evaluation. In the event the study is terminated early or shows poor clinical efficacy, completion of biomarker assessments is based on justification and intended utility of the data.

#### **8.6.1. Ex Vivo Whole Blood Cytokine Release Assay**

An ex vivo whole blood IL-23 induced cytokine release assay will be used to measure systemic PD activity from inhibition of IL-23 induced signaling as it relates to exposure to confirm systemic IL-23 pathway engagement with JNJ-77242113 with CCI in participants with psoriasis. This is an optional substudy, samples will only be collected from participants who consent (where local regulations permit).

#### **8.6.2. Serum Psoriasis Pharmacodynamic Changes**

Inflammatory mediators relevant to the pathophysiology of psoriasis including but not limited to IL-22, IL-17A, IL-17F and beta-defensin-2 will be evaluated to assess the impact of JNJ-77242113 with CCI on inflammatory proteins in the serum.

#### **8.6.3. Skin Psoriasis-Associated Gene Expression Changes**

Total ribonucleic acid will be extracted from lesional and non-lesional skin biopsies to assess impact of JNJ-77242113 with CCI on psoriasis-associated gene signatures and individual genes to better define the therapeutic response. This is an optional substudy, samples will only be collected from participants who consent (where local regulations permit).

### **8.7. Immunogenicity Assessments**

Antibodies to JNJ-77242113 will be evaluated in serum samples collected from all participants according to the SoA, Section 1.3. Additionally, serum samples should also be collected at the final visit from participants who discontinued study intervention or were withdrawn from the study. These samples will be tested by the sponsor or sponsor's designee.

Serum samples will be screened for antibodies binding to JNJ-77242113 and the titer of confirmed positive samples will be reported. Other analyses may be performed to verify the stability of antibodies to JNJ-77242113 and/or further characterize the immunogenicity of JNJ-77242113.

Serum samples will be used to evaluate the immunogenicity of anti-JNJ-77242113 antibodies. Samples collected for immunogenicity analyses may additionally be used to evaluate safety or efficacy aspects that address concerns arising during or after the study period. Genetic analyses will not be performed on these serum samples. Participant confidentiality will be maintained.

#### **Analytical Procedures**

The detection and characterization of antibodies to JNJ-77242113 will be performed using a validated assay method by or under the supervision of the sponsor. All samples collected for detection of antibodies to JNJ-77242113 will also be evaluated for JNJ-77242113 serum concentration to enable interpretation of the antibody data. Antibodies may be further characterized and/or evaluated for their ability to neutralize the activity of the study intervention(s). Samples may be stored up to 15 years (or according to local regulations) following

the last participant's last visit for the study at a facility selected by the sponsor to enable further analysis of immune responses to JNJ-77242113.

## 8.8. Medical Resource Utilization and Health Economics

Health Economics/Medical Resource Utilization and Health Economics parameters are not evaluated in this study.

## 9. STATISTICAL CONSIDERATIONS

Statistical analysis will be done by the sponsor or under the authority of the sponsor. A general description of the statistical methods to be used to analyze the efficacy and safety data is outlined below. Specific details will be provided in the SAP.

### 9.1. Statistical Hypotheses

The hypothesis of this study is that an oral tablet formulation of JNJ-77242113 will result in superior efficacy compared with placebo as determined by the proportion of participants achieving PASI 75 response at Week 16.

### 9.2. Sample Size Determination

This study is designed to assess the clinical response, safety/tolerability, and pharmacology of JNJ-77242113 CCI in participants with moderate-to-severe plaque psoriasis. The sample size is evaluated based on the primary endpoint of a PASI 75 response at Week 16. The sample size of 80 participants was chosen in order to have sufficient power to detect a difference between the JNJ-77242113 CCI (30 participants for each of low and high dose groups) and the placebo group (20 participants).

The assumptions for the sample size and power calculations were mainly based on the clinical data from guselkumab Phase 3 clinical studies that evaluated the safety and efficacy in the treatment of adult participants with moderate-to-severe plaque psoriasis.

The null hypothesis is to be tested at an overall Type 1 error rate of 0.10 (2-sided). Assuming PASI 75 response rates at Week 16 are 5% to 10% for placebo and 40% to 80% for JNJ-77242113 CCI, a sample size of 20 participants in the placebo group and 30 participants in the JNJ-77242113 CCI dose groups will provide at least 90% power to detect a 35% difference between the JNJ-77242113 CCI and placebo groups in the proportion of participants achieving PASI 75 response at Week 16 based on a 2-sample Z-test.

### 9.3. Populations for Analysis Sets

For the efficacy analyses in this study, the full analysis set (FAS) will be used according to the participants' assigned treatment to which they were randomized, regardless of the treatment they received. The FAS includes all randomized participants who receive at least 1 administration of study intervention. The FAS will be used for all primary and secondary efficacy analyses.

Safety analyses will include all randomized participants who received at least 1 administration of study intervention and participants will be analyzed based on the treatment they actually received,

regardless of the treatment groups to which they were assigned. Pharmacokinetics analyses for JNJ-77242113 will include all randomized participants who receive at least 1 complete dose of JNJ-77242113 CCI and have at least 1 valid blood sample drawn for PK analysis after their first dose of JNJ-77242113 CCI. Antibodies to JNJ-77242113 will be analyzed for all randomized participants who receive at least 1 dose of JNJ-77242113 CCI and have at least 1 sample obtained after the first dose of JNJ-77242113 CCI for the detection of antibodies to JNJ-77242113.

For purposes of analysis, the following populations are defined:

Population	Description
Enrolled	All participants who sign the ICF.
Randomized	All participants who were randomized in the study.
FAS	All randomized participants who take at least 1 dose of study intervention.
Safety Analysis Set	All randomized participants who take at least 1 dose of study intervention.
PK Analysis Set	All randomized participants who take at least 1 complete dose of study intervention and had at least 1 valid blood sample drawn for PK analysis after their first dose of study intervention.
Immunogenicity Analysis Set	All randomized participants who take at least 1 complete dose of study intervention and had at least 1 sample obtained after their first dose of study intervention.

## 9.4. Statistical Analyses

### 9.4.1. General Considerations

An overall Type I error rate of 0.10 (2-sided) will be used for statistical testing. No multiplicity control methods will be applied to the secondary endpoints in this Phase 2a study. Nominal p-values will be calculated for all comparisons. Descriptive summary statistics, such as n, mean, standard deviation (SD), median, interquartile range, minimum, and maximum for continuous variables, and counts and percentages for discrete variables will be used to summarize most data.

### 9.4.2. Primary Endpoint(s)

To assess the primary endpoint of a PASI 75 response at Week 16, comparisons between each of the JNJ-77242113 with CCI groups compared with placebo will be performed using a Cochran-Mantel-Haenszel (CMH) test stratified by the baseline weight ( $\leq 90$  kg,  $>90$  kg).

#### 9.4.2.1. Estimand

The primary estimand (ie, a precise definition of the primary targeted treatment effect) is defined by the following 5 attributes:

#### Study intervention:

- 10 mg JNJ-77242113 CCI, oral tablet administered once a day
- 50 mg JNJ-77242113 CCI, oral tablet administered once a day

- Placebo, oral tablet administered once a day

**Population:** adult participants with moderate-to-severe plaque psoriasis

**Variable/endpoint:** Response binary variable, where a responder is defined as a participant achieving a PASI 75 response at Week 16 who does not have intercurrent events in categories 1 to 2 (defined below).

**Intercurrent Events (ICEs) and their corresponding strategies**

ICEs	Analysis Strategy for Addressing Intercurrent Events
1. Discontinuation of study intervention due to lack of efficacy or due to an AE of worsening of psoriasis	Composite Strategy: Participants with these intercurrent event are considered as PASI 75 non-responders after these events, and prior to Week 16. The occurrence of these intercurrent events is captured in the variable definition.
2. Initiation of a protocol-prohibited medication or therapy during the study that could improve psoriasis	
3. Any discontinuation of study intervention for reasons other than ICE 1	Treatment Policy: observed data will be used regardless of whether or not this intercurrent event had occurred.

Note: For participants experiencing multiple ICEs, ICE 2 will override ICE 3.

**Population level summary:** Difference in the proportions of participants achieving a PASI 75 response at Week 16 between the JNJ-77242113 with **CCI** and placebo intervention groups.

### Primary Endpoint Analysis

In the primary efficacy analysis, data from all randomized participants who received at least 1 administration of study intervention will be analyzed according to their assigned treatment group.

The primary endpoint will be based on CMH test stratified by baseline weight category ( $\leq 90$ kg,  $>90$ kg). The proportion difference between JNJ-77242113 **CCI** groups and placebo group and its 2-sided 95% confidence interval (CI) will be provided based on normal approximation with Mantel-Haenszel weights adjusting for baseline weight category.

To examine the robustness of the primary endpoint analysis, additional analyses will be conducted using different missing data approaches; these analyses will be described in the SAP. In addition, sensitivity analyses will be performed for the primary endpoint using the per protocol population, which includes participants who are generally compliant with the protocol. To evaluate the consistency of the efficacy, subgroup analyses of the primary endpoint will be performed.

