### 5.3.3. Analysis Methods

#### 5.3.3.1. Analysis Methods for the Primary Estimand

The primary endpoint will be analyzed based on the primary estimand and the data from all participants in FAS will include data from all randomized participants who received at least one administration of study intervention based on their assigned intervention group, regardless of the actual intervention received.

Comparisons of each JNJ-77242113 treatment group versus the placebo group will be performed for the primary endpoint of PASI 75 at Week 16. The Cochran-Mantel-Haenszel chi-square statistic stratified by baseline weight category ( $\leq 90$  kg,  $> 90$  kg) at a 2-sided significance level of 0.1 will be used. Difference in response rates between each of the active groups and the placebo group adjusted for baseline weight category ( $\leq 90$  kg,  $> 90$  kg) using Mantel-Haenszel weight and the corresponding 90% CI will be presented. Pairwise comparisons will not be adjusted for multiplicity.

Participants with ICEs 1-2 before Week 16 will be considered as PASI75 non-responders at Week 16. Participants with ICE 3, observed PASI data after this ICE will be utilized in the analysis. After accounting for the ICEs for the primary estimand, participants with the missing data of the primary endpoint at Week 16 will be considered as non-responders.

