##### 5.4.2.1. Binary Endpoints

The binary secondary endpoints at Week 16 will be analyzed using the estimand described in section 5.4.1.2. The analysis strategy for ICEs and missing data will be handled in the same manner as the primary estimand for the primary analysis. The proportions of participants achieving the above secondary efficacy endpoints will be summarized for each intervention group.

The Cochran-Mantel-Haenszel chi-square statistic stratified by baseline weight category ( $\leq 90$  kg,  $> 90$  kg) at a 2-sided significance level of 0.1 will be used. Difference in response rates between each of the active and placebo groups at Week 16 adjusted for baseline weight category ( $\leq 90$  kg,  $> 90$  kg) using Mantel-Haenszel weight and the corresponding 90% CI will be presented.

The Fisher's Exact test will be used for treatment comparisons in binary response endpoints. The proportion differences between JNJ-77242113 groups and placebo and the exact confidence intervals will be provided.

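### The normal-approximation Mantel-Haenszel interval for the primary PASI 75 difference covers about 2 points too little on average over the planned response rates; a stratified score interval would largely correct this

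*Protocol*

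**What the plan says.** Protocol 9.4.2.1 (Primary Endpoint Analysis) tests PASI 75 at Week 16 with a CMH test stratified by weight category. It adds the difference in proportions with a two-sided 95% interval "based on normal approximation with Mantel-Haenszel weights adjusting for baseline weight category".

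SAP 5.3.3.1 keeps the CMH test at two-sided 0.10 and presents the adjusted difference "using Mantel-Haenszel weight and the corresponding 90% CI will be presented". It does not repeat the words on normal approximation, but it names no other method, and SAP Appendix 2 (Section 6.2) records no change from the protocol. Neither document names the variance estimator or discusses small-sample coverage.

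Exact methods appear only in SAP 5.4.2.1, under the secondary binary endpoints: "The proportion differences between JNJ-77242113 groups and placebo and the exact confidence intervals will be provided".

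The design values are in Protocol 9.2: "a sample size of 20 participants in the placebo group and 30 participants in the" dose groups, with "response rates at Week 16 are 5% to 10% for placebo and 40% to 80" per cent for active treatment.

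**The concern.** A normal-approximation interval estimates its standard error from the observed proportions. Twenty placebo participants at 5-10% give one or two expected responders. If there are none, the simple variance assigns the placebo arm zero variance. High active response rates add skewness in the other arm. Under these conditions a Wald-type interval tends to be too narrow and badly centred.

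What is at stake is the stated precision of the main effect estimate. The difference in proportions is the population-level summary of the primary estimand, and the interval is what a reader of a proof-of-concept trial uses to judge how small the benefit might be.

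**Working it through.** **Inputs.** From the documents: 20 placebo and 30 active participants per comparison; placebo 5-10% and active 40-80%; two weight strata; Week 16 missing data counted as non-response, so the denominators stay at 20 and 30. Assumed, because the documents give no split of the 80 participants by weight: 40/40, 48/32 and 56/24.

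**The plan's own figure.** Protocol 9.2 states "at least 90% power to detect a 35% difference between the" groups, "based on a 2-sample Z-test", at two-sided 0.10. With unpooled variance, power = Φ(Δ/SE − 1.645), where SE = √[p0(1−p0)/20 + p1(1−p1)/30].
- 5% vs 40%: SE = √(0.002375 + 0.008) = 0.1019; Φ(3.436 − 1.645) = 96.3%.
- 10% vs 45%: SE = √(0.0045 + 0.00825) = 0.1129; Φ(3.100 − 1.645) = 92.7%.

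Exact binomial power is 94.8% and 90.2%, so the stated figure is reproduced. The pooled-variance version gives 91.8% and 87.6%, the second 2.4 points short.

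**No placebo responders.** 0.95^20 = 35.8% at a 5% rate; 0.90^20 = 12.2% at a 10% rate.

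**Intervals compared.** In stratum j, w = n1·n0/N and d = Σw(p̂1 − p̂0)/Σw.
- Simple (Greenland-Robins) variance: Σw²[p̂1(1−p̂1)/n1 + p̂0(1−p̂0)/n0]/(Σw)².
- Sato variance: (d·ΣP + ΣQ)/(Σw)², with P = [n1²x0 − n0²x1 + n1n0(n0−n1)/2]/N² and Q = [x1(n0−x0) + x0(n1−x1)]/(2N).
- Stratified Miettinen-Nurminen: all δ with (d−δ)² ≤ z²·Σw²·[N/(N−1)]·[p̃1(1−p̃1)/n1 + p̃0(1−p̃0)/n0]/(Σw)², where p̃ are the maximum-likelihood rates constrained to p̃1 − p̃0 = δ.

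**Coverage.** The binomial probabilities of all outcomes whose interval contains the true difference were summed, without simulation. The grid was placebo 5-10% by 0.5 point and active 40-80% by 1 point (11 × 41 = 451 rate pairs), with rates equal across strata. Figures below span the three splits.

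| Interval | 90%: mean (range) | 95%: mean (range) |
|---|---|---|
| MH, simple variance | 87.3-87.4% (83.6-89.5%) | 92.6-92.7% (88.8-94.3%) |
| MH, Sato variance | 88.1% (83.8-90.1%) | 93.2% (89.0-95.0%) |
| Stratified Miettinen-Nurminen | 90.0-90.1% (88.8-91.6%) | 95.3% (94.4-96.3%) |

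At 95%, both Mantel-Haenszel intervals fall below nominal at all 451 pairs. At 90%, the simple variance does so at all 451 and Sato at 447-448. The largest shortfalls are 90 − 83.6 = 6.4 and 95 − 88.8 = 6.2 points.

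**Pattern over the rates** (40/40 split, 90% level, Sato): 89.7% at 5% vs 70%, 85.7% at 5% vs 80%, 89.3% at 10% vs 60%, 88.2% at 10% vs 80%. Coverage oscillates because the outcomes are discrete.

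**Direction of misses** (40/40 split). Averaged over the grid at 90%, the simple-variance interval lies wholly above the true difference 8.2% of the time and wholly below it 4.4%; for Sato, 7.8% and 4.1%. At 10% vs 80% and the 95% level, the simple-variance interval lies above 8.8% of the time and below 1.3%.

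**Sensitivity.** More extreme or slightly imbalanced splits gave similar results. In 16 settings with rates differing by stratum, 90% coverage was 86.4-88.9% (simple), 87.2-89.8% (Sato) and 89.9-93.0% (score).

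**Agreement with CMH.** At δ = 0 the score statistic above equals the CMH chi-square without continuity correction, so the score interval excludes zero exactly when CMH rejects at the matching level. At 10% vs 40%, the simple-variance interval disagrees with CMH in 4.1% of trials at the 90% level and 9.5% at the 95% level.

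**The case against.** The strongest reply is that little depends on this interval. The primary conclusion comes from the stratified CMH test at two-sided 0.10, and no decision rule in the documents uses the interval. An average shortfall of about 2 points in a standard method, in an 80-participant Phase 2a study with nominal p-values, is then a refinement. That stands as to severity. It does not make the reported precision right.

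The score interval is also not exact. At the 90% level it reaches nominal at only about 53% of the rate pairs, and single pairs fall up to 1.2 points below (0.6 at 95%). That stands too: the gain is near-nominal coverage on average, with much smaller departures.

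Three stronger readings are tempting but unsupported. A reader might infer that the efficacy test is compromised; it is not, because CMH does not use this interval. A reader might infer that coverage worsens steadily as active response rises, or is acceptable only near 40-45%; the oscillation shown above contradicts this. A reader might infer greater harm for rare-response endpoints such as PASI 100 or IGA 0; the documents give no rates for these, and SAP 5.4.2.1 already adds exact intervals for the secondary binary endpoints.

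**Conclusion.** The concern holds at modest severity. The planned interval under-covers over the protocol's own response range with either variance: by 1.9-2.7 points on average at 90% and 1.8-2.4 at 95%, and by about 6 points at the worst rate pairs. The error mostly favours the drug, since the lower limit tends to lie too high.

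This rests on four assumptions: the planned group sizes and rates; an assumed stratum split, which barely changes the figures; equal rates across strata, relaxed with similar results; and reading the SAP's interval as the protocol's normal approximation, since no other method is named. The sample size, the CMH test and the point estimate are not in question.

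**What to change.** In Protocol 9.4.2.1 and SAP 5.3.3.1, specify a stratified Miettinen-Nurminen score interval with Mantel-Haenszel weights by weight stratum, and state that the variance carries the N/(N−1) factor. Without that factor, mean coverage is only about 89.1-89.4% at the 90% level and 94.8% at the 95% level. Keep the CMH p-value and the Mantel-Haenszel point estimate.

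Use one confidence level in both documents: the protocol says 95% and the SAP 90%. The 90% level matches the plan's error rate ("The null hypothesis is to be tested at an overall Type 1 error rate of 0.10 (2-sided"). Record the change in SAP Appendix 2.

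The cost is one sentence in each place and a modestly wider interval. Mean width rises by 3.5-6.4% over the simple variance and 1.4-4.3% over Sato at 90%; at 95%, by 3.9-8.2% and 1.7-6.1%. The mean lower limit falls by about 0.02-0.04 (90%) or 0.03-0.06 (95%). Compared with the simple variance, the chance that the 90% interval excludes zero falls from 95.5% to 93.5% at 5% vs 40%, and from 83.5% to 79.4% at 10% vs 40%; for the 95% interval, from 92.4% to 86.3% and from 76.4% to 66.9%. Sample size, the CMH test and its power do not change.
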